5.4 STRATEGIES FOR RECRUITMENT AND RETENTION

A detailed recruitment and retention plan will be maintained by the Sponsor.

5.5 PARTICIPANT WITHDRAWAL OR TERMINATION

5.5.1 REASONS FOR WITHDRAWAL OR TERMINATION

As the study treatment requires only a single injection, best efforts will be made to encourage subjects to attend all follow-up visits. Subjects will be informed that they are free to withdraw

from the study at any time and for any reason. A premature discontinuation from study will occur when a subject who signed informed consent ceases participation in this study, regardless of circumstances, prior to completion of the defined study period. Subjects can be prematurely discontinued from the study for one of the following reasons:

- Death
- Lost to follow-up after a minimum of 3 attempts have been made to contact the subject, including sending a registered letter
- Subject withdraws consent
- TEAE
- Subject non-compliance
- Request by regulatory authority
- Study terminated by Sponsor

The Investigator may remove a subject from the study if, in the Investigator's opinion, it is not in the best interest of the subject to continue in the study.

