Detailed instructions for obtaining and managing the radiographs will be provided to the investigational center prior to the initiation of subject enrollment. The intent (as described in the Image Review Charter – Image Acquisition Guidelines) is that radiographs should be obtained in the posterior-anterior (PA) view, whenever possible.

All radiographs will be submitted to an independent radiologist who will document disease stage according to the Kellgren-Lawrence grading scale for compliance with inclusion/exclusion criteria, as well as JSW for efficacy assessments.

Widespread Pain Index and Symptom Severity (WPI&SS) Form

The WPI&SS assessment consists of a body map that determines a subject's areas of pain or tenderness [Widespread Pain Index (WPI)] and symptom severity (SS) questions ([Clauw 2014](#)). A WPI&SS assessment will be completed by the subject at Screening Visit 1 on paper.

Upon completion of the WPI&SS assessment, the subject will sign/initial and date the source document to indicate that the assessments are reported accurately.

The WPI&SS assessment sheets will be provided by the Sponsor and may not be reproduced.

Electronic Diary Device Provision and Training

Electronic diary device provision will occur at Screening Visit 2. Subjects will be trained on electronic diary and questionnaire completion at Screening Visit 2. Subject training will include details on what medications are NSAIDs. Detailed instructions for subject training and electronic questionnaire completion will be provided to the investigational center. Electronic devices are to be returned to the site at Week 24 (EOS)/ET.

Electronic devices will store completed questionnaire data for up to 30 days. Therefore, it is recommended that site personnel review study subject ePRO data and compliance reports in the ePRO vendor web portal (StudyWorks) at least once a week or more frequently as needed to ensure timely subject completion and transmission of questionnaire data between study visits.

Pain Numeric Rating Scale (NRS)

The pain NRS is an 11-point scale (0-10) for subject self-reporting of average knee pain in the last 24 hours. A pain NRS for each knee will be completed daily by the subject during the screening period from Screening Visit 2 until Day 1 to assess subject ability to be compliant with a daily pain assessment. During the screening period, daily pain NRS assessments will be

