completed by subjects in the evening (between 5:00 pm and 11:59 pm) remotely on their electronic devices for each knee to collect average knee pain in the last 24 hours. Subject electronic diary compliance for daily pain NRS over the screening period will be reviewed at Day 1 prior to randomization. After screening, starting on Day 1, daily pain NRS assessments are to be completed by subjects in the evening (between 5:00 pm and 11:59 pm) remotely on their electronic devices for the target knee only. Refer to [Section 7.3.7](#) for a schedule of electronic diary and questionnaire completion.

Subjects will complete the pain NRS on the Sponsor-provided electronic device. Subjects will receive notifications reminding them to complete the daily pain NRS assessment. If a subject does not complete the electronic diary for pain NRS for at least 4 out of 7 days in a given week, this will be considered a protocol deviation due to subject non-compliance, but the subject should not be removed from the study unless the Investigator determines it is in the best interest of the subject.

Increases in pain should only be considered TEAEs if reported by the subject, regardless of pain NRS scores.

Nonsteroidal Anti-Inflammatory Drugs (NSAIDs) Electronic Diary

The daily electronic diary of NSAID usage will document subject usage of any NSAID medication as “yes” or “no” in response to the following question, “Did you take any medication that is an NSAID in the last 24 hours?”. Starting on the day of Screening Visit 2 after the site visit, daily electronic diary of NSAID usage is to be completed by subjects in the evening (between 5:00 pm and 11:59 pm) remotely on their electronic devices. Refer to [Section 7.3.7](#) for a schedule of electronic diary and questionnaire completion.

Subjects will complete electronic diary of NSAID usage on the Sponsor-provided electronic device. Subjects will receive notifications reminding them to complete the electronic diary of NSAID usage. If a subject does not complete the electronic diary of NSAID usage for at least 4 out of 7 days in a given week, this will be considered a protocol deviation due to subject non-compliance, but the subject should not be removed from the study unless the Investigator determines it is in the best interest of the subject.

Western Ontario and McMaster Universities Arthritis Index (WOMAC)

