7.3.5 EARLY TERMINATION VISIT

If possible, the following procedures and assessments should be performed within 14 days of subject premature withdrawal or termination:

- Collection of TEAE and concomitant procedures/therapies/medication data
- Review of medical history
- Vital signs measurements (pulse, blood pressure, respiration rate, and temperature)

- Physical examination, including knee examination of both knees
- Weight measurement
- Venipuncture and collection of samples for clinical laboratory tests
- Radiograph – bilateral in weight-bearing fixed flexion position, posterior-anterior (PA) view X-ray
- Physician Global Assessment
- Evaluation of success of blinding
- Return of electronic device

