8.3 TIME PERIOD AND FREQUENCY FOR EVENT ASSESSMENT AND FOLLOW-UP

The reporting period for TEAEs starts after the injection of study medication on Day 1 and ends after the final study visit.

TEAEs must be followed until resolution by the Investigator. Resolution is defined as the return to baseline status or stabilization of the condition with the expectation that it will remain chronic. TEAEs that are not serious and are ongoing at the subject's last visit will be followed until the

study close-out visit, if requested. Serious adverse events that are not resolved or stabilized during this time period will be followed until resolution or stabilization.

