10.6.3 BREAKING THE STUDY BLIND/PARTICIPANT CODE

The blind may be broken by a qualified physician who is an Investigator in this study in the event of a medical emergency in which knowledge of the identity of the study medication is critical to the management of the subject's immediate course of treatment. Before breaking the blind, the Investigator should determine that the information is necessary (i.e., that it will alter the subject's immediate course of treatment).

If deemed necessary to break the blind for a study subject, the Samumed Medical Monitor is to

be contacted to obtain concurrence. If it is not possible to contact the Medical Monitor beforehand, he or she should be contacted as soon as possible after breaking the blind for a subject. Details regarding the emergency unblinding will be documented in Medidata Balance and medical records. Instructions on how to unblind treatment assignment will be provided to each Investigator and kept within a guidance document at each site. No other site users will have access roles to Balance that will allow treatment assignment unblinding.

Any subject whose blind has been broken will continue their follow-up visits as per protocol.

In circumstances when the blind is unintentionally broken at the investigational center, the breaking of the blind should be reported to the designated Sponsor unblinded Clinical Research Associate as soon as possible after breaking the blind for a subject.

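### Ending participation early takes back the diary device, so remotely entered Week 24 endpoints are lost for early leavers after a one-time injection, and two listed reasons for leaving need not end follow-up

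*Protocol*

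**What the plan says.** Protocol 5.5.1 opens with a retention aim: "As the study treatment requires only a single injection, best efforts will be made to encourage subjects to attend all follow-up visits". It then says "Subjects can be prematurely discontinued from the study for one of the following reasons". The list mixes reasons that necessarily end follow-up (death, loss to follow-up, withdrawn consent, termination by a regulator or the sponsor) with two that need not: a TEAE, and "Subject non-compliance". A separate sentence lets the Investigator remove a subject when continuing is not in that subject's best interest.

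Two other sections are more protective. Under 7.1.1, completing the pain NRS or NSAID diary on fewer than 4 of 7 days is a protocol deviation, "but the subject should not be removed from the study unless the Investigator determines it is in the best interest of the subject". Under 10.6.3, "Any subject whose blind has been broken will continue their follow-up visits as per protocol".

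Section 5.5.2 sends anyone who discontinues after Day 1 to the Week 24/ET procedures within 14 days, if possible. On the device, 7.1.1 says "Electronic devices are to be returned to the site at Week 24 (EOS)/ET", and the ET list in 7.3.5 includes "Return of electronic device". That list has a radiograph, laboratory tests, examinations and the Physician Global Assessment, but no pain NRS, WOMAC or Patient Global Assessment (PTGA). Nothing describes reduced or remote-only participation.

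SAP 9.4 does not impute for the main efficacy analyses. It adds LOCF and MMRM as sensitivity analyses for weekly pain NRS, WOMAC Pain, WOMAC Function and PTGA.

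**The concern.** When treatment is complete on Day 1, neither an adverse event nor poor compliance can stop study drug. Discontinuing for either reason stops data collection only. The unqualified non-compliance item also conflicts with 7.1.1, which keeps a subject with poor diary compliance in the study unless leaving is in that subject's best interest.

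Weekly pain NRS, WOMAC Pain, WOMAC Function and PTGA are all entered on the device away from the clinic. A subject who wants no more visits could still supply them, but the only exit described removes the means of doing so.

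At stake is the Week 24 comparison that supports dose selection. A pain increase reported by the subject can itself be a TEAE (7.1.1), so that reason for leaving may be related to the endpoint. Missing Week 24 values could then be informative, and each one costs precision.

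**Working it through.** **No planning figure to reproduce.** The only one is about 630 subjects in six equal arms (Protocol 10.5), so 630/6 = 105 per arm. No effect size, SD, power or dropout rate is given, and 630 cannot be rebuilt. The structural point does not depend on it.

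**Which data are lost**

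1. By the week definition in SAP 5.2.1, Week 24 runs from Day 1 + 7×23 = 162 to Day 7×24 = 168. A weekly NRS needs at least 4 of 7 entries.
2. Entries are made from 5:00 pm. Assuming the device is handed back earlier in the day, return on Day 165 leaves only Days 162, 163 and 164: three entries, one too few. Return on or before Day 165 therefore means no Week 24 NRS.
3. Week 24 WOMAC and PTGA are due on the evening of Day 167 or 168 (7.3.7). Return on or before Day 167, with nothing completed earlier that week, means neither exists.
4. SAP 9.2 assigns ET assessments to Week 24 only within Day 169 +7, that is Days 169 to 176. That window opens after the diary days, so it recovers none of these endpoints.
5. Medial JSW is imaged at ET but counts as Week 24 only inside the same window. It needs a visit, so keeping the device would not help it.

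**Bias in the treatment contrast (assumed inputs)**

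Let d be the share of an arm lost and g how much worse leavers would have been than those observed, in SD. Each observed arm mean is too favourable by d×g, so the bias of active against vehicle is

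b = d_a·g_a − d_v·g_v.

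With s = √[1/(105(1−d_a)) + 1/(105(1−d_v))], the chance of a nominal two-sided p below 0.05 when there is no effect is 1 − Φ(1.96 − b/s) + Φ(−1.96 − b/s).

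| Lost, active / vehicle | Leavers worse by (SD), active / vehicle | b (SD) | Chance of p < 0.05 |
|---|---|---|---|
| 10% / 10% | 1 / 1 | 0.10 − 0.10 = 0 | 0.050 |
| 10% / 5% | 0.5 / 0.5 | 0.050 − 0.025 = 0.025 | 0.053 |
| 10% / 5% | 1 / 1 | 0.10 − 0.05 = 0.05 | 0.064 |
| 15% / 5% | 0.5 / 0.5 | 0.075 − 0.025 = 0.05 | 0.064 |
| 15% / 5% | 1 / 1 | 0.15 − 0.05 = 0.10 | 0.105 |
| 10% / 10% | 1 / 0 | 0.10 − 0 = 0.10 | 0.106 |

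**Precision (assumed inputs)**

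- The standardized difference with 80% power at 105 per arm is (1.960 + 0.842)×√(2/105) = 0.387 SD. Power for it falls to 78% at 5% loss, 76% at 10% and 71% at 20%.
- The standard error grows by 1/√(1−d) − 1: 2.6% at 5% loss and 8.5% at 15%. If half of those subjects kept answering remotely, effective losses of 2.5% and 7.5% give 1.3% and 4.0%.

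**The case against.** The list is permissive, and 5.5.2 uses it partly to record a reason on the eCRF. The retention aim, the 7.1.1 restriction and 10.6.3 should all keep its use rare. A missed visit is not a discontinuation, since 5.5.1 requires that the subject cease participation, and nothing says that missing visits ends the diary. Section 5.4 also refers to a retention plan outside these documents. All of this stands as a reason to expect few cases. It does not say what happens to a subject who stops visits but would go on answering, and the only route described ends with the device returned.

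The SAP does not ignore dropout: LOCF and MMRM use data up to exit, and that softens the loss. However, LOCF assumes no change after exit and MMRM assumes missing at random, so neither covers dropout driven by worsening that was never recorded.

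Three stronger readings are tempting and are not supported:

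- **That outcomes are lost selectively in subjects who did badly.** The documents give no dropout rate, no split by reason and no outcomes for leavers. Protocol 2.3.1 reports one phase 1 dose-limiting toxicity of increased knee pain, judged probably related, but does not say that the subject withdrew. Protocol 2.2 reports no obvious dose response or difference from placebo in AEs leading to withdrawal in the earlier phase 2 trial, which used three of the same doses. The link to outcome is weaker still for non-compliance.
- **That a shift in one arm's mean is the bias.** If 2 to 6% leave and would have been 1 to 3 NRS points worse, that arm's mean moves by 0.02×1 = 0.02 to 0.06×3 = 0.18 points. An equal shift under vehicle cancels it.
- **That safety follow-up simply stops.** Section 8.3 says "The reporting period for TEAEs starts after the injection of study medication on Day 1 and ends after the final study visit", so events that begin after exit are not captured. The same section requires the Investigator to follow TEAEs to resolution, although it then follows non-serious events still ongoing at the last visit only until close-out, if requested. Serious events are followed until resolved or stable, and the ET visit collects TEAEs and laboratory tests.

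**Conclusion.** The point holds as a gap in data capture and an inconsistency between sections. Subjects who leave before the last days of Week 24 lose their Week 24 values for three of four primary endpoints and PTGA, although these could be entered without a visit, and the main ANCOVA uses observed data only. The consequence is a risk of informative missingness and a modest loss of precision; bias is not demonstrated. The contrast bias is 0 if leavers are alike in share and outcome across arms. It is 0.025 to 0.10 SD if 10 to 15% leave active against 5% leaving vehicle and leavers are 0.5 to 1 SD worse in both arms. These shares and differences are assumptions, and the one relevant statement about the earlier trial gives no support for a difference between arms. The case for change rests on its low cost.

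**What to change.** - **Protocol 5.5.1:** reconcile the list with 7.1.1 and 10.6.3. Separate reasons that necessarily end follow-up from those that need not, and qualify the non-compliance item so that it agrees with 7.1.1. Leave the Investigator's best-interest clause and all medical care as they are.
- **Protocol 5.5.2 and 7.3.5:** state that a subject who stops clinic visits without withdrawing consent keeps the device and continues the remote pain NRS, WOMAC and PTGA through Day 168. Still record the reason for stopping visits, including TEAE, on the eCRF, so that disposition tables keep it.
- **SAP 6.3:** say whether such a subject counts as having completed the study for the per-protocol set. The main ANCOVA needs no change.
- **Optional:** have full leavers complete WOMAC and PTGA before returning the device. These values would inform sensitivity analyses only.

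The cost is protocol and consent wording and longer device loans for a few subjects. The change recovers nothing from subjects who withdraw consent or are lost to follow-up.

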5.5.2 HANDLING OF PARTICIPANT WITHDRAWALS OR TERMINATION

In case of premature discontinuation of study participation, Week 24 (EOS)/ET procedures should be conducted within 14 days of discontinuation for any subject who discontinues after the Day 1 visit, if possible. The date the subject is withdrawn from the study and the reason for the discontinuation should be recorded on the eCRF. The Investigator or designee must complete all applicable eCRF pages for subjects who discontinue from the study prematurely.

Replacement of subjects who withdraw or discontinue prematurely is not allowed.

5.6 PREMATURE TERMINATION OR SUSPENSION OF STUDY

The Investigator and the Institutional Review Board/Ethics Committee (IRB/EC) reserve the right to prematurely terminate the study in the interest of subject safety and welfare. The Sponsor reserves the right to prematurely terminate the study at any time for administrative or safety reasons. Written notification, documenting the reason for study suspension or termination, will be provided by the suspending or terminating party to the Investigator, Sponsor, and regulatory authorities as appropriate. If the study is prematurely terminated or suspended, the Investigator will promptly inform the IRB and will provide the reason(s) for the termination or suspension.

6. STUDY AGENT

6.1 STUDY AGENT(S) AND CONTROL DESCRIPTION

6.1.1 ACQUISITION

Samumed will be responsible for the manufacturing, labeling, packaging, distribution, reconciliation, and destruction of study medication product and vehicle product related to the study.

6.1.2 FORMULATION, APPEARANCE, PACKAGING, AND LABELING

SM04690 drug substance is an off-white powder. SM04690 drug product is a sterile suspension in diluent containing 0.5% carboxymethylcellulose sodium and 0.05% polysorbate 80 in pH 7.4 phosphate buffered saline. SM04690 drug product is supplied as 2.4 mL of formulated suspension in a 3 mL Type I glass vial. A separate 3 mL Type I glass vial contains 2.4 mL of vehicle to be used as a diluent. SM04690 vehicle product contains 0.5% carboxymethylcellulose sodium and 0.05% polysorbate 80 in pH 7.4 phosphate buffered saline. The placebo will be vehicle only or a sham injection.

SM04690 and vehicle are manufactured by PrimaPharma, Inc. (San Diego, CA) and will be supplied as single-use injections. SM04690 and vehicle will be supplied to the study pharmacist and labeled according to the applicable local and country regulations. For dispensing, dose preparation, and labeling instructions, refer to the Pharmacy Manual.

6.1.3 PRODUCT STORAGE AND STABILITY

The study medication and vehicle must be stored at the appropriate temperature (15°-30°C or 59°-86°F) and in a restricted area with limited access. Temperature excursions are allowed between 2°-60°C (36°-140°F) for a time period not to exceed a cumulative of 72 hours.

6.1.4 PREPARATION

Each dose will be prepared by taking a known volume of SM04690 drug product and adding to a vehicle (diluent) vial, mixing well to re-suspend the product, then injecting 2 mL intra-articularly into the target knee. Refer to the Pharmacy Manual for detailed instructions on study medication preparation.

6.1.5 DOSING AND ADMINISTRATION

SM04690 will be administered in the following dosage strengths:

- SM04690 0.03 mg in 2 mL Injectable Suspension
- SM04690 0.07 mg in 2 mL Injectable Suspension
- SM04690 0.15 mg in 2 mL Injectable Suspension
- SM04690 0.23 mg in 2 mL Injectable Suspension
- SM04690 0 mg; 2 mL vehicle injection only
- SM04690 0 mg; 0 mL sham injection (intra-articular injection procedure is performed identically to all other treatment groups but without the injection of any liquid)

Each subject will be consented and randomized using a permuted block design to 1 of 6 treatment arms at Day 1. The injectable investigational product or vehicle, or the sham injection is to be administered by the unblinded Investigator as a 1-time single injection into the target knee joint. Only 1 knee will be treated for each subject in this study. Although not required, the injection may be guided by ultrasound if it is the standard practice of the Investigator.

Only topical anesthetic (absolutely no invasive anesthetic) is allowed for the study injections.

Anesthetic, if used, may not be combined with the study medication prior to injection.

Prior to administration of the intra-articular knee injection, the subject should be blinded to observation of the study medication and injection procedure according to the processes specified in the Site-Specific Blinding Plan.

The unblinded Investigator (injector) should place the needle into the joint and, while not required, if it is the standard practice of the Investigator, a small amount (0.3-0.5 mL) of joint fluid can be aspirated (if present) in order to confirm correct needle placement; the aspirated fluid does not need to be re-injected. Thereafter, the total volume contained in the syringe is to be injected into the joint space of subjects that were randomized to either active or vehicle arms. In subjects randomized to sham injection (only intra-articular positioning of the needle without volume application), while not required, if it is the standard practice of the Investigator, a small amount (0.3-0.5 mL) of joint fluid can be aspirated (if present) in order to confirm correct needle placement. The duration that the needle remains inside the joint as well as the pressure that is applied should be similar to the active and vehicle injections in order to minimize subject awareness that they are receiving a sham injection. Unblinded Investigators (injectors) participating in the trial should also inform subjects that they may or may not feel any sensation related to the injection.

